9.2.2 Secondary Endpoints

The secondary endpoints are defined in section 3.3.2. These will be analyzed using the ITT and PP samples.

- Proportion endpoints will be descriptively summarized using frequency tables with frequencies, percentages, and 95% confidence intervals. Chi-squared tests will be used for comparisons between operationally tolerant and non-tolerant participants.
- Time-to-event endpoints will be assessed using Kaplan-Meier survival estimates and associated two-sided 95% confidence intervals. Subjects lost to competing risks or lost to follow-up will be censored at the time of occurrence of these events.
- Continuous endpoints will be summarized using descriptive statistics (n, mean, standard deviation, median, minimum, maximum). T-tests will be used for comparisons between operationally tolerant and non-tolerant participants.
- Categorical endpoints will be summarized using counts (n) and percentages (%). Chi-squared tests will be used for comparisons between operationally tolerant and non-tolerant participants.

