9.5 REPORTING DEVIATIONS FROM THE ORIGINAL STATISTICAL PLAN

The principal features of both the study design and the plan for statistical data analysis are outlined in this protocol and in the statistical analysis plan (SAP). Any change in these features requires either a protocol or an SAP amendment, which is subject to review by the DSMB, the study sponsor(s), and the health authorities. These changes will be described in the final study report as appropriate.

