7.3. Secondary Endpoints

All secondary endpoints will be analyzed as described in Table 7-2. Mock displays for these results are outlined in the Appendix.

Table 7-2 Table of Endpoints and Analysis Methods

Endpoint	Method	Population
Primary		
The proportion of participants who achieve operational tolerance 52 weeks after completion of immunosuppression withdrawal.	Proportion of participants who achieve operational tolerance 52 weeks after completion of immunosuppression withdrawal with a corresponding two-sided 95% exact binomial confidence interval.	ITT, PP
Secondary		
Safety		
The proportion of participants who develop DSA or de novo anti-HLA antibodies after initiation of immunosuppression withdrawal.	Proportion of participants who develop DSA or de novo anti-HLA antibodies after initiation of immunosuppression withdrawal with a corresponding two-sided 95% exact binomial confidence interval.	ITT, PP
The incidence, severity, and timing of acute rejection, steroid resistant rejection, and chronic rejection.	
Acute Rejection: Incidence will be measured as the proportion of participants who have acute rejection (per Banff criteria) with a corresponding two-sided 95% exact binomial confidence interval.
 
Severity will be measured according to the Banff grade. Acute rejection can be expressed as mild, moderate or severe. This will be summarized descriptively with counts and percentages.
	ITT, PP
	
Steroid Resistant Rejection: Incidence will be measured as the proportion of participants who have steroid resistant rejection (rejection requiring antibody treatment) with a corresponding two-sided 95% exact binomial confidence interval.
 
All steroid resistant rejections are considered severe in nature and nothing further will be summarized.
	
	
Chronic Rejection: Incidence will be measured as the proportion of participants who have chronic rejection (per Banff criteria) with a corresponding two-sided 95% exact binomial confidence interval.
	

	
Severity will be measured according to the Banff grade. Chronic rejection can be expressed as early or late. This will be summarized descriptively with counts and percentages.
 
For all rejection types, timing will be expressed as the time from the initiation of immunosuppression withdrawal to the time of the first biopsy showing acute rejection and will be summarized descriptively.
 
All data presented will use the central read.

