The incidence and progression of graft fibrosis in tolerant versus non-tolerant patients.	
Fibrosis will be looked at in two ways—by ISHAK ITT, PP and LAFSc.
 
ISHAK is a measure taken directly from the central pathology read.
 
LAFSc is calculated as the sum of three measures that summarize fibrosis in the portal tract (portal_fibrosis per central read), sinusoids (disse_fibrosis per central read), and centrilobular vein (central_fibrosis per central read).
 
For both ISHAK and LAFSc, a subject will be considered as having graft fibrosis if the score is greater than or equal to 2.
 
Incidence of graft fibrosis will be summarized descriptively with a proportion and corresponding two-side 95% exact binomial confidence interval using Ishak Score and LAFSc, separately, for tolerant and non-tolerant subjects.
 
Change in ISHAK score from baseline biopsy to the last available biopsy will be calculated. Descriptively statistics will be calculated separately for tolerant and non-tolerant subjects. This same process will be repeated for LAFSc.
 
All scores utilized will be from the central read.

The incidence of graft loss.	Proportion of participants who have lost their liver graft with a corresponding two-sided 95% exact binomial confidence interval. ITT, PP
The incidence of all-cause mortality.	Proportion of participants who have died with a corresponding two-sided 95% exact binomial confidence interval. ITT, PP

The incidence of study-related SAEs.	Proportion of study-related SAEs as assessed by the NIAID Medical Monitor with a corresponding two-sided 95% exact binomial confidence interval.	ITT, PP
Efficacy		
The proportion of operationally tolerant subjects who remain free of rejection at 3 years after completing immunosuppression withdrawal.	Proportion of tolerant participants who remain off all IS and free of rejection 3 years after completing immunosuppression withdrawal with a corresponding two-sided 95% exact binomial confidence interval.	Tolerant Subjects

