Changes in renal function (defined as estimated GFR calculated by CKD-EPI) in tolerant versus non-tolerant participants at 1, 2 and 3 years after completing immunosuppression withdrawal for tolerant subjects and failure of withdrawal for non-tolerant subjects.	
Baseline eGFR will be calculated from data collected at Visit 0. If Visit 0 data is missing, Visit -1 data will be used. Data collected closest to 1-year post completion/failure, within +/- 2 months, will be used to calculate eGFR at 1. The same process will be followed for 2 and 3-years after completion/failure.
 
eGFR will be calculated using the CKD-EPI equation:
 $\text{GFR} = 141 * \min(\text{Scr}/\kappa, 1)^\alpha * \max(\text{Scr}/\kappa, 1)^{-1.209} * 0.993^{\text{Age}} * 1.018 \text{ [if female]} * 1.159 \text{ [if black]}$ 
Scr: serum creatinine (mg/dL) κ: 0.7 for females and 0.9 for males α: -0.329 for females and -0.411 for males
 
Change in eGFR will be calculated as: 1-year post completion/failure eGFR – baseline eGFR
 
Thus positive value will indicate increase kidney function.
 
Changes will be summarized descriptively by tolerance status.
	ITT, PP
Changes in Quality of Life in tolerant versus non-tolerant participants and in all participants at baseline versus the end of study participation, as measured by the NIDDK Liver Transplantation Database Quality of Life Form.	The questionnaire filled out at Visit 0 will serve as the baseline questionnaire. The questionnaire filled out closest to the end of study participation will serve as the end of study questionnaire. For subjects	ITT, PP

	
with complete follow-up, this will be the questionnaire completed at Visit 208 or Visit 306.
 
The questionnaire will be summarized into five domains as outlined by Bell et al. The domains include measures of disease, psychological status, personal function, social and role function, and general health perception.
 
The change in each domain will be calculated as: Domain Score at End of Study – Domain score at Baseline.
 
The baseline, end of study, and change from baseline domain scores will be summarized descriptively by tolerance status.
 
If the data permits, a spaghetti plot visualizing each component score over time will be produced. Each graph will have two panels—one depicting the tolerant subjects, the other depicting the non-tolerant subjects.
	

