Changes in SF-36 (see Appendix 6) in tolerant versus non-tolerant participants and in all participants at baseline versus the end of study participation.	
The questionnaire filled out at Visit 0 will serve as the baseline questionnaire. The questionnaire filled out closest to the end of study participation will serve as the end of study questionnaire. For subjects with complete follow-up, this will be the questionnaire completed at Visit 208 or Visit 306.
 
The SF-36 questionnaire will be scored in accordance with the scoring algorithm (Version 2 scoring algorithm used via quality metric) and summarized with the Physical Component Score (PCS) and Mental Component Score (MCS).
 
The change in the component scores will be calculated as: Component Score at End of Study – Component Score at Baseline.
 
The baseline, end of study, and change from baseline domain scores will be summarized descriptively by tolerance status.
 
If the data permits, a spaghetti plot visualizing each component score over time will be produced. Each graph will have two panels—one depicting the tolerant subjects, the other depicting the non-tolerant subjects.
	ITT, PP

Predictive value and the correlative value of the following parameters with regard to operational tolerance:
 
a. Time post-transplant
 
b. Recipient age
	
A logistic regression model will be utilized to estimate the probability of operational tolerance. Time post-transplant and recipient age will be included in the model as continuous covariates. Odds ratios and 95% confidence intervals will be presented.
	ITT, PP
---	--	---------

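### The SAP replaces the protocol's tolerant versus non-tolerant comparisons with separate group summaries, gives no estimate of any difference, and does not record the change

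*SAP*

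**What the plan says.** Protocol 9.2.2 sets the method by type of endpoint. For continuous endpoints: "T-tests will be used for comparisons between operationally tolerant and non-tolerant participants". For proportion and categorical endpoints: "Chi-squared tests will be used for comparisons between operationally tolerant and non-tolerant participants".

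SAP 7.3 then takes over: "All secondary endpoints will be analyzed as described in Table 7-2". Four secondary endpoints in that table are worded as tolerant versus non-tolerant:

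- **eGFR change at years 1, 2 and 3:** "Changes will be summarized descriptively by tolerance status".
- **NIDDK quality-of-life form and SF-36:** "The baseline, end of study, and change from baseline domain scores will be summarized descriptively by tolerance status".
- **Graft fibrosis, change in Ishak score and LAFSc:** "Descriptively statistics will be calculated separately for tolerant and non-tolerant subjects".
- **Graft fibrosis, incidence:** a proportion with an exact 95% interval in each group.

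The mock tables in the SAP appendix have Tolerant, Non-tolerant and Total columns, with changes shown as median and IQR. They have no column or row for a difference. SAP Section 3 gives rounding rules for t, z and p-values, but no test is attached to any endpoint.

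On changes to the principal features of the plan, protocol 9.5 says: "Any change in these features requires either a protocol or an SAP amendment". In the public text, SAP Section 11, which is headed for changes from the protocol's analyses, has nothing under its heading.

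**The concern.** These endpoints name a contrast between two groups. The protocol planned to examine it; the SAP sets the groups side by side and stops. Readers would have to compare two medians by eye, or judge whether two intervals overlap. Neither shows how large the difference is or how precisely it is known.

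The two documents also disagree on method, with no recorded reason. If the descriptive approach was deliberate, the SAP should say so. If it was an oversight, it should be corrected before the tables are produced.

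**Working it through.** **1. Does the design foresee a two-group comparison at this size?** Protocol 9.3 gives a mean difference of 0.1155, a pooled SD of 0.152, a 5% level, and 24 tolerant of 60 at 40% tolerance; it states power 0.808.

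- Standardised difference: 0.1155 / 0.152 = 0.76.
- √(1/24 + 1/36) = 0.2635, so the noncentrality is 0.76 / 0.2635 = 2.88.
- A two-sided t-test on 58 degrees of freedom has power 0.809, against the stated 0.808.

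The figure reproduces, and the other rows of that table agree within 0.002. It concerns a biomarker, which is left to the separate mechanistic plan. The documents give no SD or power for eGFR, quality of life or fibrosis.

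**2. Precision of the missing contrast.** With complete data and a common SD, the 95% half-width for a difference in means, in SD units, is t(0.975, 58) × √(1/n₁ + 1/n₂), with t = 2.002.

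| Tolerant / non-tolerant | Half-width (SD) |
|---|---|
| 18 / 42 (30% tolerant) | 0.56 |
| 24 / 36 (40%) | 0.53 |
| 30 / 30 (50%) | 0.52 |

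For eGFR change at 24 / 36, assumed SDs of 10, 15 and 20 mL/min (not in the documents) give about ±5.3, ±7.9 and ±10.5 mL/min. Dropouts would widen all of these.

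**3. Can separate group intervals stand in for the difference?** Take assumed fibrosis counts of 5/24 tolerant and 18/36 non-tolerant.

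- Separate exact 95% intervals: 7.1% to 42.2% and 32.9% to 67.1%. They overlap.
- Difference: 20.8% − 50.0% = −29.2 points; Newcombe 95% interval −48.5 to −4.1; uncorrected chi-squared p = 0.023.

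So overlapping group intervals can hide a difference whose own interval excludes zero. The counts are illustrative only.

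**4. Can a reader rebuild the contrast?** Not from the mock tables for the change scores, since a median and IQR do not give a mean difference or its standard error. SAP Section 3 lists mean and SD among its default summaries, but the displays do not carry them.

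**The case against.** The strongest defence is that tolerance is itself an outcome. The groups form after baseline, and the SAP counts eGFR years from completion of withdrawal for tolerant participants and from failure for non-tolerant ones. A contrast between them is not a treatment effect, and a purely descriptive report is a respectable choice. This stands as a reason to prefer an estimate over a p-value and to label it an association. It does not explain leaving out the contrast that the endpoints name, and the SAP does not offer it as a reason.

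The protocol also promises tests, not differences with intervals. That is so: the estimate goes a little beyond the protocol, which is why it needs recording. Protocol 9.5 accepts an SAP amendment, and the SAP's front matter is not in the public text. A breach of procedure therefore cannot be inferred, only that no explanation is visible.

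A reader might infer more than the documents support:

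- **That no precision is reported.** Fibrosis incidence has an exact interval in each group. What is missing is the interval for the difference.
- **That the objective on renal function and quality of life cannot be answered.** Protocol 2.2 asks about the impact of withdrawal. Everyone in the ITT sample begins withdrawal, so the change from baseline in the Total column bears on it directly.
- **That the last-questionnaire rule is an error.** The SAP says "The questionnaire filled out closest to the end of study participation will serve as the end of study questionnaire", which carries out an endpoint that both documents define at the end of participation, not at week 156.
- **That baseline-adjusted models are required.** Between non-randomised groups, adjusted and unadjusted differences can estimate different things. For fibrosis change, participants who fail during withdrawal have no scheduled biopsy (Protocol Appendix 3), while those who complete it have biopsies at weeks 52 and 156 (Appendix 2). The last available biopsy can thus fall at very different times.

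**Conclusion.** The inconsistency is real. The protocol plans comparisons for these four secondary endpoints, the SAP has none, and the public text gives no reason. The missing interval for a difference in mean change would be about ±0.53 SD at 24 versus 36, and 0.52 to 0.56 SD for 30% to 50% tolerant, assuming 60 participants, complete data and equal SDs.

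The primary endpoint is untouched, and so is the age and time-since-transplant analysis, which already has odds ratios with intervals. This is a gap worth closing in secondary reporting, not a flaw in the design. The estimates would describe association only.

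**What to change.** In SAP Table 7-2 and the mock tables:

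1. Add the tolerant minus non-tolerant difference in mean change, with the 95% CI that matches the protocol's t-test, for eGFR at years 1, 2 and 3, each NIDDK quality-of-life domain, and the SF-36 physical and mental component scores.
2. Add a difference in proportions with a 95% CI (for example Newcombe) for fibrosis incidence, by Ishak score and by LAFSc.
3. Label all of these as associations, because tolerance status is determined after baseline and follow-up starts at completion or at failure of withdrawal.
4. State that participants in safety follow-up have no scheduled biopsy, so the timing and availability of biopsies differ by group. Keep the fibrosis change scores descriptive.
5. Record in SAP Section 11 that these estimates replace the tests in protocol 9.2.2, and why.

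Baseline-adjusted models, or a mixed model for the questionnaires read at week 156, are optional sensitivity analyses.

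The cost is an SAP amendment, a few lines of code and a few table rows, with no new data collection. The downside is small: the intervals will be wide.

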APPENDIX 3-C. (COVID-19 MODIFIED) SCHEDULE OF EVENTS – SAFETY FOLLOW-UP

Safety Follow-up Weeks ¹	0	13	26	52	104	156
Visit Number ²	301 ³	302	303	304	305	306
General Assessments						
Quality of Life Questionnaires ⁴					X	X
Telephone consultation ⁵	X-----					X
ECG			Prior to restarting tacrolimus if on MMF monotherapy ^{6,7}			
Local Clinical Laboratory Assessments						
LFTs ⁸					Every 12 weeks	
CBC w/differential					X	X
Comprehensive metabolic panel, includes LFTs					X	X

¹ The assessments outlined in Appendix 3 should be completed for all participants who initiated but did not complete immunosuppression withdrawal. Follow-up should begin within 2 weeks of the date of immunosuppression withdrawal failure (see section 3.1.3.5).

² If a for-cause liver biopsy is needed, follow Appendix 5.

³ For any participant requesting early termination from the study, collect the following assessments if possible: telephone consultation with AE and concomitant medication update, CBC with diff, and comprehensive metabolic panel including LFTs.

⁴ Complete Quality of Life assessment by mail.

⁵ Complete following the performance of each liver function test assessment done outside of a transplant center clinical visit; AEs and concomitant medications to be reviewed.

⁶ Perform locally or at study site, as necessary.

⁷ For participants on MMF monotherapy who need to restart tacrolimus for biopsy-confirmed rejection or presumed acute rejection (see section 6.8). A follow-up ECG will be performed within 7 days after tacrolimus has been restarted. ECG findings will be monitored per the site's standard of care until the subject is taking a stable dose of tacrolimus. Evidence of a prolonged QTc interval will be appropriately evaluated and treated.

⁸ If participant experiences a rejection episode, complete liver function tests per standard of care until resolution as determined by the investigator. Record all liver function tests performed during a rejection episode in EDC.

APPENDIX 4. SCHEDULE OF EVENTS—ADDITIONAL, CONCURRENT FOLLOW-UP FOR PARTICIPANTS WHO RESTART IMMUNOSUPPRESSION AFTER SUCCESSFUL COMPLETION OF IMMUNOSUPPRESSION WITHDRAWAL - THESE VISITS ARE TO OCCUR CONCURRENTLY WITH THE VISITS OUTLINED IN APPENDIX 2

IMPORTANT NOTE: For the duration of the COVID-19 pandemic, do not follow this Appendix.

Additional Follow-Up Weeks ¹	26
Visit Number ^{2,3}	RIS ⁴
General Assessments	
Limited physical exam	X
Vital signs including weight	X

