7.1.2. Assessment Time Windows

Unscheduled visits may also occur throughout the study.

All data will be included in analyses, regardless of time of assessment, unless explicitly stated.

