7.2.1. Computation of the Primary Endpoint

A participant will be considered operationally tolerant if they have successfully withdrawn from all immunosuppression and remain off all immunosuppression for 52 weeks, have no evidence of rejection since enrollment, and have a liver biopsy at 52 weeks read centrally that shows both

the absence of rejection and has histological stability consistent with Table 1. Otherwise, the participant will be considered non-tolerant.

Participants who are non-evaluable at 52 weeks following discontinuation of all immunosuppression time point due to inadequate follow-up, lack of biopsy, or premature study termination will be considered non-tolerant for the purpose of evaluating the primary endpoint.

Biopsy results may be as early as 44 weeks following the discontinuation of all immunosuppression. This is because a for-cause liver biopsy visit that occurs within 8 weeks prior to a scheduled protocol visit takes the place of a scheduled protocol visit, thus a for-cause biopsy within 8 weeks of Visit 204 can be evaluated for the primary endpoint. Any biopsies done earlier than 44 weeks prior to discontinuation of all immunosuppression will be reviewed for inclusion by the SMT on a case by case basis. Any primary endpoint biopsy performed later than 52 weeks (+4 weeks) will be utilized.

All immunosuppression dosing information is collected as a daily record. Therefore, any immunosuppression information will not have an associated window.

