Psychological Status	X.X (X-X)	X.X (X-X)	X.X (X-X)
Personal Function	X.X (X-X)	X.X (X-X)	X.X (X-X)
Social and Role Function	X.X (X-X)	X.X (X-X)	X.X (X-X)
General Health Perception	X.X (X-X)	X.X (X-X)	X.X (X-X)

[1] Change is calculated as the difference between the last available QOL assessment and the QOL assessment collected at baseline.

Table X. Logistic Regression Model Predicting Operational Tolerance

Variable	
Time post-transplant	
Odds ratio per increase of 1 year (95% CI)	X.X (X.XX, X.XX)
Recipient Age	
Odds ratio per increase of 1 year (95% CI)	X.X (X.XX, X.XX)

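### Quality-of-life and SF-36 change runs to the last available form with no time window, so the tolerant and non-tolerant columns can cover different spans of follow-up

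*SAP*

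**What the plan says.** The quality-of-life and SF-36 rows of SAP Table 7-2 (section 7.3) use the same rule. Baseline is fixed: "The questionnaire filled out at Visit 0 will serve as the baseline questionnaire". The follow-up value is not: "The questionnaire filled out closest to the end of study participation will serve as the end of study questionnaire". One group is tied to a visit: "For subjects with complete follow-up, this will be the questionnaire completed at Visit 208 or Visit 306". The footnote to the quality-of-life mock table in the SAP Appendix puts the rule more bluntly: "Change is calculated as the difference between the last available QOL assessment and the QOL assessment collected at baseline".

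Neither row sets a window, and SAP 7.1.2 supplies none: "All data will be included in analyses, regardless of time of assessment, unless explicitly stated". The eGFR row of the same table works differently. It uses fixed points at 1, 2 and 3 years after completion or failure, and takes the nearest value within 2 months either side.

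Results are summarised by tolerance status in the ITT and PP samples. On status, SAP 7.2.1 says that participants who cannot be evaluated at week 52 because of "inadequate follow-up, lack of biopsy, or premature study termination will be considered non-tolerant" for the primary endpoint.

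**The concern.** Protocol secondary objective 3 asks what withdrawal does to quality of life, and the endpoint contrasts tolerant with non-tolerant participants. For anyone without complete follow-up, the SAP rule measures change up to whenever a form was last filled in. Leaving early also decides which column a person is in. A participant who leaves before week 52 is non-tolerant, whereas a tolerant one has by definition been followed for about a year off all drugs. Short spans therefore collect on one side of the comparison, and the mock table would not show it.

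A narrower problem sits inside this. Nothing says that the end-of-study form must come after baseline. If a participant has only the Visit 0 form, a literal reading makes it both values and records no change, although nothing was observed.

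**Working it through.** **1. When forms are scheduled (Protocol appendices).**
- Appendix 1A (withdrawal): Visit 0, and Visit 109 for mycophenolate users only.
- Appendix 2 (withdrawal completed): weeks 0, 26, 52, 78, 104, 130 and 156.
- Appendix 3 (withdrawal not completed): weeks 0, 26, 52, 104 and 156.

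After week 0, the follow-up weeks common to Appendices 2 and 3 are 26, 52, 104 and 156.

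**2. Time from Visit 0 to the form used.** The withdrawal phase lasts about 24 to 45 weeks, and Visits 201 and 301 fall within 2 weeks of completion or failure.
- Tolerant, last form at Visit 204: 24 + 52 = 76 to 45 + 52 = 97 weeks.
- Tolerant, last form at Visit 208: 24 + 156 = 180 to 45 + 156 = 201 weeks.
- Leaves during the taper, last form at Visit 301: up to about 45 + 2 = 47 weeks, and only a few weeks if failure comes early.

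All of these enter the same table as change to end of study.

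**3. Who could have no post-baseline form.** Protocol 4.3.1 asks a participant leaving before completion to stay in Appendix 3 follow-up, and failing that to attend a termination visit equal to Visit 301, which includes the questionnaires. Those left without a form are participants who die, are lost, decline that visit as well, or miss the forms. The documents do not say how many to expect.

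**4. Effect of one artificial zero.** Protocol 9.3 uses 40% tolerance in 60 participants, that is 24 tolerant and 36 non-tolerant. As a check on that split, the exact (Clopper-Pearson) 95% interval for 24/60 is 27.56% to 53.46%, matching the stated 27.6% to 53.5%.

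With k zeros among n non-tolerant participants:
- reported mean change = (1 − k/n) × mean among those with a post-baseline form;
- reported median = μ + Φ⁻¹(0.5 / (1 − k/n)) in SD units while this is below zero, if true changes are normal with mean μ and SD 1.

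For n = 36 and an assumed μ = −0.5 SD:

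| k (assumed) | Mean multiplied by | Shrinkage | Median (SD units) |
|---|---|---|---|
| 0 | 1.000 | 0% | −0.50 |
| 1 | 0.972 | 2.8% | −0.46 |
| 2 | 0.944 | 5.6% | −0.43 |
| 3 | 0.917 | 8.3% | −0.39 |
| 4 | 0.889 | 11.1% | −0.34 |
| 6 | 0.833 | 16.7% | −0.25 |

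The median is included because the mock table reports median and IQR. With 42 non-tolerant participants (30% tolerance), each zero costs 1/42 = 2.4% of the mean and six cost 14.3%. With 24 (60% tolerance), the figures are 1/24 = 4.2% and 25%.

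**5. Early but real forms.** A form at Visit 301 or 201 is an observed change. It may be larger or smaller than that person's week-156 change would have been, so no formula gives its direction.

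**The case against.** The case against has real weight.

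- **Visit 0 as end of study is an inference from silence.** Table 7-2 names a baseline form and an end-of-study form, and SAP section 3 bars imputation unless explicitly stated. On that reading, a participant with only Visit 0 has no change score. This stands as the more natural intention. But section 3 also lets specific rules override the general ones, and the last-form rule is specific, so a programmer would have to choose.
- **Few people are affected.** A reader might infer that early leavers in general get a zero. The documents do not support that. The regular termination visits include the forms, and under Protocol 3.1.3.5 and 6.8 participants whose withdrawal fails stay in follow-up, which runs to Visit 306 or 208.
- **The pandemic schedules.** Appendix 3-C shows no questionnaire before week 104 and Appendix 2-C none before week 52, and the early-termination list in both is "telephone consultation with AE and concomitant medication update, CBC with diff, and comprehensive metabolic panel including LFTs". A reader might infer that the gap is built in. But 2-C also has no week-52 biopsy and 3-C has no blood count or metabolic panel before week 104. Both look written for participants already past those visits, who would have had forms due under Appendix 2 or 3.
- **The SAP follows the protocol.** The protocol endpoint compares baseline with the end of participation, so replacing it by week 156 would alter the endpoint. This stands, and the fix keeps the protocol's summary.
- **The other forms are not wholly unused.** Plots of scores over time are planned if the data permit. They do not repair the numeric summary.
- **The analysis is descriptive.** That is true of the SAP, although Protocol 9.2.2 plans t-tests of tolerant against non-tolerant for continuous endpoints.

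**Conclusion.** The concern holds in a limited form. For participants without complete follow-up, the SAP uses the last available form, with no window and no stated post-baseline requirement. Because leaving before week 52 makes a participant non-tolerant, very early values fall almost entirely in that column, and the columns can cover different spans of time.

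The size and direction of the resulting bias cannot be determined from the documents. The one calculable part is that each artificial zero would shrink a 36-person mean change by 2.8%. This assumes the 24/36 split and a literal reading of the rule, and the number of such participants is unknown. A zero would mute a loss or a gain alike.

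Two further inferences should be resisted. Zeros are not strictly confined to the non-tolerant group: a tolerant participant who missed every later form would also receive one, and zeros enter the Total column too. Nor do forms from Visits 201 and 301 add further dilution. They are observed changes at a different time, of unknown direction.

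No figure in the plan is wrong on this point. It is an inexpensive improvement to the analysis of a secondary endpoint, using forms already scheduled.

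**What to change.** In both rows of Table 7-2 and in the mock-table footnote:

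1. State that only a form completed after baseline may serve as follow-up, and that a participant without one has no change score.
2. Report change at weeks 26, 52, 104 and 156 with a stated window and time origin (completion or failure), as the eGFR row does for its yearly points.
3. Preferably estimate these from a repeated-measures model using all scheduled forms, with baseline score, visit, tolerance status and status by visit.
4. Keep the protocol's last-available-form summary alongside, and show by tolerance status how many forms were used and when they were completed.

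The cost is SAP wording and one extra model per score. The model assumes that forms are missing at random given the earlier ones, and the week-156 intervals will be somewhat wider. No new data collection is needed.
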